## Sample

A consecutive, non-probabilistic sample will be performed. The participants will be included sequentially as they are admitted to the clinic, with their voluntary agreement to participate in the study.

## OUTCOMES

### Primary Outcome

Proportion of patients with clinical improvement of premature ejaculation, defined as a tripling of the baseline time (without treatment), as measured by the IELT (intravaginal ejaculation latency time) during the therapy and three months after completion.

### Secondary Outcomes

The patient presents a change in the PDET score.

The magnitude of the change in the PEDT score.

Type, frequency and severity of adverse events during the therapy.

## OUTCOME VARIABLES

Since the aim is to evaluate possible changes in the length of time of the appearance of the ejaculatory reflex, two tools will be used to quantify this datum: the PDET and IELT (Appendix 1). The first is a questionnaire that evaluates the perception the patient has of his situation, and the second will be measured with a timer which the patient will use to document the time it takes between vaginal penetration and the appearance of ejaculation, data which must be recorded on the in-home chart (Appendix 2) which each patient will have and which he must bring to each follow-up appointment. These data will be used to quantify the following variables:

- IELT and PEDT at week 6 of the protocol (halfway point).
- IELT and PEDT at the end of treatment.
- IELT and PEDT three months after finishing the protocol.

### Other variables of interest

Variable	Conceptual Definition	Operational Definition	Measurement Scale
Age	Time between birth and the interview date	Number of years completed	Quantitative

Frequency of sexual relations	Number of sexual relations in one week	Number of relations per week	Quantitative
Alcohol consumption	Frequency and amount of alcoholic beverages consumed	0. Occasional 1. Frequent	Qualitative
Consumption of psychoactive drugs	Natural or synthetic chemical substances that affect the central nervous system when consumed.	1. Psycho-depressants 2. Psycho-stimulants 3. Cannabis 4. Opiates 5. Opioids 6. Volatile.	Nominal Qualitative
Baseline IELT	Average intravaginal latency time before beginning therapy, based on measurements taken during two weeks prior to beginning treatment	Seconds	Quantitative
Baseline PEDT	Score from the premature ejaculation diagnostic scale before beginning treatment	Score from 0 to 20	Quantitative

### Data Analysis Plan

A descriptive analysis will be performed of the sociodemographic and clinical characteristics of the research subjects. For the categorical variables, absolute and relative frequencies will be estimated. For the numerical variables, central tendency and dispersion measurements will be estimated.

To evaluate the efficacy of this new therapy, the proportion of patients whose illness improves will be estimated and compared with the expected proportion proposed by the hypothesis (30%). Improvement is defined as the tripling of the baseline (without treatment) intravaginal latency time.

The safety will be evaluated by estimating the incidence of adverse events experienced by the patients during the study. These will be classified by the degree of severity according to WHO criteria.

The analyses will be performed with Stata 14.

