## JUSTIFICATION

Premature ejaculation is a condition which affects roughly 25% of the male population, creating problems in their sexual life and affecting their quality of life. (1)

Although a variety of pharmacological and therapeutic treatments exist today, they have several drawbacks that limit their long-term use, such as: undesirable secondary effects from tricyclic antidepressants and selective and non-selective serotonin reuptake inhibitors, risk of dependence with the chronic use of opioid analgesics and a high transfer rate with topical anesthetics which requires the use of condoms. (10-12)

Given the results obtained from using posterior tibial neurostimulation for several pelvic pathologies, including urge incontinence and some reported cases of chronic pelvic pain, and considering the physiology and anatomy of these structures, it is feasible that the use of this therapy for patients with primary premature ejaculation will have beneficial effects. There are three reasons for this: 1) The parasympathetic reflex is inhibited, primarily affecting the expulsion stage of ejaculation; 2) Since these stages are regulated by the autonomic nervous system and are linked with it, a sympathetic effect on emission could be achieved, generating a global delay in the start of the ejaculatory reflex; 3) Since ejaculation is also controlled at the supraspinal level, and considering studies of urinary incontinence performed by Finazzi-Agro (22) which show evidence of changes in evoked potential produced at the frontal cortex level after stimulating the posterior tibial nerve, suggesting changes at the cortex level and explaining the long-term control of incontinence, if our hypothesis is correct we could expect to see a change not only during the percutaneous electrostimulation of the posterior tibial nerve but it could also be prolonged over time.

The present study will make it possible to identify whether neurostimulation of the posterior tibial is beneficial for patients with premature ejaculation, as well as to determine the risks associated with this therapy. This evidence will serve as a basis for subsequent comparative studies to evaluate the best treatment options, thereby providing an opportunity to offer patients more treatment options, possibilities and alternatives to complement or substitute current treatments.

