## RESEARCH HYPOTHESIS

**Null hypothesis:** No clinically significant improvement in ejaculation time exists for patients who are treated with Transcutaneous Posterior Tibial Nerve Stimulation (TPTNS)

**Alternative hypothesis:** Clinically significant improvement in ejaculation time exists for patients who are treated with Transcutaneous Posterior Tibial Nerve Stimulation (TPTNS).

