#### **Sample size**

The "single stage procedure" proposed by Fleming was used to estimate the sample size for this type of trial. For  $P_0=10\%$  and  $P_1=30\%$  with an alpha error of 5% and a beta of 80%, 18 patients need to be included in order to prove the study's hypothesis. After adjusting this number by a percentage of loss of 30%, which is observed in daily practice, 24 patients will be included in the study.

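### The efficacy analysis sets the response rate against the planning target of 30% instead of the null rate of 10%, and gives no test or success rule

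*Combined protocol and SAP*

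**What the plan says.** The Sample size section names Fleming's single-stage procedure, sets P0 = 10% and P1 = 30%, and continues "with an alpha error of 5% and a beta of 80%, 18 patients need to be included". The 18 are then raised to 24 for a 30% loss. The purpose given for the 18 is a test: "18 patients need to be included in order to prove the study's hypothesis".

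The Research Hypothesis section puts the hypotheses in words only. The null reads "No clinically significant improvement in ejaculation time exists for patients who are treated", with no proportion attached. The Primary Outcome section defines a responder as a man whose latency time triples from baseline, but sets no response rate that would count as success.

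The Data Analysis Plan has one sentence on how efficacy is judged: the proportion improved will be estimated and "compared with the expected proportion proposed by the hypothesis (30"%). The 10% figure does not appear there. Nor does a named test, an alpha, a sidedness, a confidence interval or a number of responders needed.

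**The concern.** In a Fleming single-stage design the data are tested against P0. P1 is only the rate at which the chance of success is calculated. Here the analysis takes P1 as its reference, so it does not address the hypothesis that the sample size was calculated for.

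The trial has one arm, so this fixed rate is its only comparator. Because no decision rule is given, the comparison can be read in several ways, and these err in opposite directions: some fail a therapy that is exactly on target, and one passes a therapy at the rate the design treats as uninteresting. The reading could also be chosen after the data are seen. The Justification section says of the result: "This evidence will serve as a basis for subsequent comparative studies". An undefined verdict would carry into those studies.

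**Working it through.** **Inputs.** From the Sample size section: P0 = 0.10, P1 = 0.30, alpha 5%, 18 men needed, 30% loss, 24 enrolled. The stated beta of 80% is read as 80% power. From the Data Analysis Plan: reference rate 0.30. Sidedness is not stated; one-sided is assumed, as is standard for Fleming's design, and the two-sided case is shown at the end.

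**The plan's own figure.** The normal-approximation formula is

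n = [(z₀.₉₅·√(P0(1−P0)) + z₀.₈₀·√(P1(1−P1))) / (P1−P0)]²

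= [(1.645 × 0.300 + 0.842 × 0.458) / 0.20]² = 19.3, rounded up to 20.

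The plan's 18 is within two patients of this. The two-sided version gives 23.7, rounded up to 24. So 18 fits a one-sided test with 10% as the null. The enrolment figure is 18 × 1.3 = 23.4, rounded up to 24.

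**Three readings of a comparison with 30%** (exact binomial, X = number of responders):

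| Reading | n = 18 | n = 24 |
|---|---|---|
| (a) One-sided 5% superiority over 30%: cut-off | ≥10 | ≥12 |
| P(success), true rate 30% | 2.1% | 3.1% |
| (b) Observed rate at least 30%: cut-off | ≥6 | ≥8 |
| P(success), true rate 30% | 46.6% | 43.5% |
| P(success), true rate 10% | 0.6% | 0.2% |
| (c) Not significantly different from 30% (two-sided exact 5%): accepted range | 2–9 | 3–11 |
| P(accepted), true rate 10% | 55.0% | 43.6% |

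For (a), one responder fewer would exceed 5%: P(X ≥ 9 | 18, 0.30) = 0.060 and P(X ≥ 11 | 24, 0.30) = 0.074. None of the three combines about 5% error at a true 10% with 80% power at a true 30%.

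**One result, different verdicts.** Take 5 responders of 18 (27.8%):

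- (a) fails: one-sided p against 30% = 0.67.
- (b) fails: 27.8% is below 30%.
- (c) passes: two-sided p against 30% = 1.0.
- The design's own null is rejected: P(X ≥ 5 | 18, 0.10) = 0.028.

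**The test against 10%** (one-sided exact, 5%). The cut-off is 5 responders for n = 15–20 and 6 for n = 21–27.

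| Evaluable men | Cut-off | Type I error at 10% | Power at 30% |
|---|---|---|---|
| 15 | 5 | 1.3% | 48.5% |
| 17 | 5 | 2.2% | 61.1% |
| 18 | 5 | 2.8% | 66.7% |
| 24 | 6 | 2.8% | 77.1% |
| 25 | 6 | 3.3% | 80.7% |

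A 30% loss from 24 leaves 24 × 0.7 = 16.8, about 17 men. The smallest n with exact power of at least 80% is 25.

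**Matching interval.** At 5/18 the two-sided 90% exact interval is 11.6–49.8% and excludes 10%, in agreement with the one-sided 5% test. The 95% interval is 9.7–53.5% and includes 10%.

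**If alpha is two-sided 5%.** With 2.5% in the upper tail, the cut-offs against 10% are 6/18 (power 46.6%) and 7/24 (power 61.1%), and 5/18 would no longer reject 10%.

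**The case against.** The strongest reply is that naming Fleming's procedure with P0, P1 and alpha already implies a test against P0, and that the analysis sentence is loose drafting. It speaks only of estimating and comparing and does not set up 30% as a null. The three readings are constructions that the plan does not state. It is true that they show what could follow, not what is planned. But the Sample size section invokes Fleming only to obtain a number of patients and gives no cut-off. The analysis section does not refer back to it and names a different value. Someone following the analysis text would use 30%.

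A second objection is that sidedness is unstated and one-sided is an assumption. That is fair, and it changes the cut-offs and the verdict at 5/18. The P0/P1 design is directional and the plan's 18 lies nearer the one-sided result, so one-sided is the natural reading. Neither choice makes 30% the null.

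Third, the corrected test also misses 80% power. This is true, but the shortfall belongs to the sample size. The corrected test does hold its error below 5% at the intended null. Fleming's normal-approximation cut-offs (4/18, 5/24) would give power of 83.5% and 88.9%, but their exact type I error is 9.8% and 8.5%, above the stated 5%. Preferring the exact test is therefore a recommendation with a reason.

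Last, a cut-off alone does not settle which visit defines a responder or who counts as evaluable. Both are open in the plan. They are separate points, but must be settled before any rule can be applied.

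**Conclusion.** The concern holds. The Data Analysis Plan names the wrong reference rate for the design and gives no rule for success, and no other section repairs either. This goes beyond missing detail, because following the text as written means comparing with 30%. Depending on the reading, an on-target therapy would succeed between about 2% and 47% of the time, or a therapy at 10% would pass about half the time.

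The conclusion rests on P0 being the null, which follows from the notation and the named method, since the plan does not label it in words. The cut-offs and power figures also assume one-sided 5% and independent binomial responses. This should be corrected before the efficacy data are analysed.

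**What to change.** In the Data Analysis Plan, replace the comparison with 30% by a one-sided exact binomial test of H0: p ≤ 10% at alpha 5%, stating the sidedness. Give the cut-off: success with at least 5 responders if 15–20 men are evaluable, at least 6 if 21–27. For any other number, apply the same test (at 14 evaluable men the cut-off is 4). Report the response rate with a two-sided 90% exact interval, which agrees with the test. Keep 30% only as the planning target.

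State the properties of this test: type I error 2.8% at both 18 and 24 men, power at 30% of 66.7% and 77.1%, and 61.1% with the 17 or so left after the planned loss. Name the visit that defines a responder and the analysis denominator in the same paragraph, so that the cut-off applies to one defined count.

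The cost is a few sentences; no new data or patients are needed for the wording change. It corrects the hypothesis tested but not the power. Exact power of 80% needs 25 evaluable men, more than the 24 to be enrolled, so the sponsor must either accept and report the lower power or revise the sample size.

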## **Data Collection and Processing Techniques and Procedures**

The patients are admitted to the clinic where they receive a medical evaluation in which they are diagnosed as patients with primary PE. Once this occurs, they are invited to participate in the study by their own voluntary choice. If the patient is interested in participating, the informed consent process is conducted and the corresponding document is signed. Then, an informational email is sent to the telephone center staff responsible for investigations, so that the information required from the patient is inputted into the corresponding database for the purpose of following-up on all of the therapy and follow-up appointments.

Prior to receiving therapy, the patient will perform a two-week process in which he will measure the intravaginal latency time with a digital timer or stopwatch APP and record it on the in-home chart. This has two objectives: first, the patient adapts to the way in which he will measure this time when having sexual relations during the study; second, to have a more precise reference point for the initial IELT, which will be used as a baseline to demonstrate changes during the study protocol.

The therapy will be conducted as follows: Three (3) sessions per week for twelve (12) consecutive weeks, with a duration of 30 minutes each, with the application of 20 Hertz with a pulse amplitude of 200 MI sec. in each session. The intensity will be applied individually for each patient depending on the tolerance of the individual. In each session, it is normal to have plantar flexion of the foot and flexion of the first toe, and after the session and particularly during the first sessions there is the possibility of muscle pain, which should be tolerable. Appendices 3 and 4 provide a more detailed description of the scheme and procedure.

During the study, each patient will have an in-home chart which he must fill out after each sexual encounter and bring to each appointment. The patients will be given strict telephone follow-up calls aimed at their keeping their monthly follow-up appointments, or if not possible due to lack of time a virtual appointment will be conducted by the physician using skype or by telephone.

It is essential that each patient who is admitted into the study complies with the scheduled electrostimulation sessions. If one of the protocols is broken, the patient will be treated as a loss to follow-up since his information could be incorrect.

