## **ETHICAL ASPECTS**

The research will comply with the legal and ethical guidelines described by 1993 Resolution No. 8430 established by the Colombia Ministry of Health and other national regulations. The principles developed by the World Medical Association for research involving human subjects, as stated in the Declaration of Helsinki, will be respected and complied with as will the ethical guidelines by the Council for International Organizations of Medical Sciences (CIOMS) and the Belmont Report.

The intervention to be evaluated has been proven to be effective for other conditions having a similar physiopathology, and the published reports of scientific evidence show that the rate of adverse events is very near zero or zero. The intervention will be administered by personnel who have all of the technical skills and experience required to administer the intervention as well as to treat possible adverse events.

According to Article 11 of The Ministry of Health's 1993 Resolution No. 8430, the risk associated with the present research is considered to be higher than the minimum. In compliance with this legislation, approval will be requested from the Ethics Committee for the authorization of the development of this investigation.

Each subject will be informed of all of the possible consequences from participating in this investigation (regardless of their probability of occurrence). Informed consent will be explained and obtained, and the individual will be entirely free to decline to participate in the study without this decision having any affect on the medical care for his illness.

In addition, to address the need to protect the privacy of each research subject and his partner an instructional guide will be made available for the confidential handling of the information collected. The confidentiality of the subjects will be ensured and, therefore, the databases will be housed in the Boston Medical Group's offices and only the study's researchers will have access to them.

Lastly, the study will ensure that the researchers possess the technical competency required for conducting this study and that they have the tools needed to manage and use the research data.

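### The rule that turns a protocol breaker into a loss to follow-up has no exception for adverse events, and no safety set is defined, so adverse event incidence may be biased downwards

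*Combined protocol and SAP*

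**What the plan says.** The treatment schedule, in Data Collection and Processing Techniques and Procedures, is "Three (3) sessions per week for twelve (12) consecutive weeks", which is 36 sessions. The same section names one likely after-effect: "particularly during the first sessions there is the possibility of muscle pain, which should be tolerable". It then states "It is essential that each patient who is admitted into the study complies with the scheduled electrostimulation sessions", followed directly by "If one of the protocols is broken, the patient will be treated as a loss to follow-up since his information could be incorrect". No number of missed sessions is permitted, and no reason for missing one is recognised.

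On safety, Secondary Outcomes lists "Type, frequency and severity of adverse events during the therapy". The Data Analysis Plan says "The safety will be evaluated by estimating the incidence of adverse events experienced by the patients during the study", with grading by WHO severity criteria. The secondary objectives also cover effects on erection quality (IIFE5 and EHS) and adverse sexual effects. No section names a safety population, gives the denominator for the incidence, or says how a man classed as lost is handled in it.

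**The concern.** The loss rule and the safety analysis meet at the missed session. Muscle pain, or one of the sexual effects that the objectives ask about, is a plausible reason to miss or stop sessions. A missed session breaks the schedule, and the rule then makes the man a loss to follow-up whose information is distrusted. Being classed as lost can therefore depend on the outcome that the safety analysis is meant to measure.

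The reason given for the rule is that information may be incorrect after a breach. That may be arguable for a stopwatch time, but it is no ground for setting aside a reported adverse event.

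The Justification section says the study will determine the risks of the therapy and serve as a basis for later comparative work. Ethical Aspects expects from published reports that "the rate of adverse events is very near zero or zero". A result near zero produced by selective exclusion would look like confirmation, and with one arm there is no comparison group to expose it.

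**Working it through.** **Inputs**
- Planned enrolment 24, from 18 needed and a 30% loss allowance (Sample size).
- Sessions: 3 × 12 = 36 (Data Collection).
- Adverse event rate for this trial: not given. All event counts below are assumed.

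**The plan's own figure.** 18 × 1.30 = 23.4, rounded up to 24, which matches. The 18 is taken as stated because it does not bear on this point.

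**Men at stake.** 0.30 × 24 = 7.2, so about 7 lost and 17 retained. Counting instead from the plan's two totals gives 24 − 18 = 6 lost.

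**Formula.** Assume all 24 men receive at least one session. Let A be the men with an event, L the men classed as lost, and k the lost men who had an event.
- Incidence in all treated men: A/24.
- Incidence if the lost men are dropped: (A − k)/(24 − L).
- Incidence if they stay in the denominator but their events are not captured: (A − k)/24, a shortfall of k/24.

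**Results with L = 7, lost men dropped** (exact Clopper–Pearson 95% intervals where shown)

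| Assumed counts | All treated men | Lost men dropped | Shortfall |
|---|---|---|---|
| A = 3, k = 3 | 3/24 = 12.5% (2.7 to 32.4) | 0/17 = 0% (upper limit 19.5) | 12.5 points |
| A = 5, k = 3 | 5/24 = 20.8% (7.1 to 42.2) | 2/17 = 11.8% | 9.1 points |
| A = 7, k = 7 | 7/24 = 29.2% (12.6 to 51.1) | 0/17 = 0% (upper limit 19.5) | 29.2 points |

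With 6 lost in place of 7, the extreme case is 6/24 = 25.0% against 0/18 = 0%, a shortfall of 25.0 points.

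If the men stay in the denominator but their events are missed, the shortfall is k/24, so at most 7/24 = 29.2 points.

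**Direction.** Dropping the lost men lowers the estimate only when events are commoner among them than among the men retained. If A = 3 and none of the three is lost, dropping the 7 gives 3/17 = 17.6%, above 12.5%. The downward bias therefore rests on the link between events and missed sessions, not on loss alone. If every event is kept, enquiry continues and all treated men are counted, the bias is zero.

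**The case against.** The strongest reply is that the plan never removes anyone from the safety analysis. It counts events in the patients over the study, which can be read as all treated men. All information goes into the electronic clinical chart, and missing clinical items are to be extracted from it at the end. Being treated as a loss may be only a label for the efficacy analysis. This stands as far as it goes. A reader might infer that the safety analysis does lose the men who were harmed, or that their follow-up ends; the documents say neither. What the reply does not cover is events after the label, since no section requires further enquiry once a man is classed as lost.

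The link between events and missed sessions is also unproven. Intensity is set to what each man tolerates, the pain is expected to be tolerable, published rates are described as zero or nearly so, and men who would find attendance difficult are excluded. The 30% loss comes from ordinary practice and is not attributed to adverse events. This is fair, and it is why the figures above are a range and not an expected bias. It does not justify leaving the rule open.

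Three stronger statements should be avoided.
- Muscle pain is not the only harm in view, because the objectives also cover erection quality and sexual effects. The text says that pain is likelier after early sessions, not that it is worse then.
- This is not informative censoring in the usual sense. The analysis is a crude incidence with no time-to-event element, and the risk is selective exclusion or under-recording.
- The 29 points are a bound, not a forecast.

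Finally, Appendices 3 and 4, which describe the procedure further, were not in the text reviewed.

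**Conclusion.** The concern holds in a limited form. The safety population is undefined, and a stated rule, unrestricted in the data it covers and in the reasons it accepts, could be applied to it. If it is, men who miss sessions because of an adverse event may be selectively excluded or not asked about events, and the reported incidence would be too low.

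The possible downward bias at about 7 of 24 lost runs from none to 29.2 percentage points. The upper end assumes that every lost man had an event, no retained man did, and all the lost men were dropped. The intermediate cases use assumed counts. The reported interval would not show this bias: in the case with three events, 0/17 would be printed with an upper limit of 19.5% and nothing to indicate that three affected men were missing.

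This should be corrected before the analysis. It is inexpensive to settle, and if the sponsor always meant to count every treated man, saying so resolves most of it.

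**What to change.** In the Data Analysis Plan, define the safety set as every man who received at least one stimulation session, and count all his adverse events up to last contact, whether or not he kept to the schedule.

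In Data Collection and Processing Techniques and Procedures:
- limit the loss-to-follow-up rule to a stated efficacy set;
- say that adverse event enquiry continues for men who miss or stop sessions, through the existing telephone or virtual contacts;
- record the reason for each missed session and each discontinuation, and report these reasons alongside the incidence.

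Reconcile the safety window: Secondary Outcomes covers the therapy period, while the Data Analysis Plan covers the whole study. One window should be stated in both places.

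The cost is a few sentences, one data field, and adverse event questions added to calls whose stated aim at present is keeping appointments. The reported incidence may be higher as a result.
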